7.3.3 Treatment of the Non-target Lesion(s)

In addition to target lesion, one additional non-target lesion in a different epicardial vessel can be treated by the specific country's regulatory-approved XIENCE stent (e.g., FDA-approved/CE-marked stent/Therapeutic Goods Administration (TGA)). A non-target lesion can be treated in the case that there are two lesions and one lesion does not meet the angiographic inclusion/exclusion criteria. The non-target lesions must be treated first, prior to randomization, and the subject may then only be randomized if treatment of the non-target lesion was successful and uncomplicated, defined as final diameter stenosis $\leq 10\%$ with final TIMI-3 flow, with no residual dissection NHLBI grade \geq type B, and no transient or sustained angiographic complications (e.g., distal embolization, side branch closure), no chest pain lasting > 5 minutes,

and no ST segment elevation or depression lasting > 5 minutes. The non-target lesion will not be considered in the primary analysis.

7.3.4 Treatment Rules of the Target Lesion(s)

Prior to use, the Absorb BVS System or XIENCE should be inspected and prepared according to the IFU. The Absorb BVS System and XIENCE should be delivered and deployed per the IFU. The treatment strategy applies to all subjects in ABSORB III, including the Lead-In Phase and the Imaging Cohort.

- Treatment of a maximum of two *de novo* native coronary artery lesions, each in a different epicardial vessel.
 - If a single target lesion is treated, it must be treated by the assigned device (Absorb BVS or XIENCE). For Lead-In subjects, the target lesion will be treated only with Absorb BVS.
 - If two lesions are treated, possible combinations are as follows:
 - Two target lesions:
 - If both lesions satisfy angiographic inclusion/exclusion criteria, then both lesions must be treated by the same device that the subject was randomized to (test device: Absorb BVS or control device: XIENCE),
 - For Lead-In subjects, both target lesions will be treated with Absorb BVS

OR

- One target lesion and one non-target lesion:
 - If only one lesion satisfies angiographic inclusion and exclusion criteria then this lesion must be treated by the assigned device (test device: Absorb BVS or control device: XIENCE) as a target lesion and the other lesion must be treated by XIENCE as a non-target lesion per the *instructions for use* (IFU).
 - The non-target lesion must be treated first (before randomization) with a XIENCE, and the patient may then only be randomized if treatment of the non-target lesion was successful and uncomplicated, defined as final diameter stenosis $\leq 10\%$ with final TIMI-3 flow, with no residual dissection NHLBI grade \geq type B, and no transient or sustained angiographic complications (e.g., distal embolization, side branch closure), no chest pain lasting > 5 minutes, and no ST segment elevation or depression lasting > 5 minutes. Please refer to **Figure 2** in **Appendix V**.
 - For Lead-In subjects, one target lesion and one non-target lesion treatment is allowed. The target lesion must be treated by Absorb BVS, and the non-target lesion must be treated by XIENCE. The non-target lesion must be treated first and successfully (as defined above) before treating the target lesion with Absorb BVS.

Access Site and Guide Catheter Size:

- Either femoral or radial access may be used.
- A minimum 6F guide catheter or greater must be used during the index procedure per requirements for Absorb BVS implantation.
 - Minimum guiding catheter compatibility (inner diameter) for Absorb BVS is 0.070"/1.8 mm (6F) (refer to IFU).
 - Devices (i.e., guide sheaths such as the GuideLiner) that decrease the inner diameter of the guide catheter outside of the Absorb BVS minimum guide catheter compatibility must not be used with the Absorb BVS System. Do not insert a 5-in-6, or a 6-in-7 guide sheath into a 6F or 7F guiding catheter, respectively, as doing so will result in an inner diameter that is too small for use with the Absorb BVS.
 - If a guide sheath is necessary, the inner diameter must meet or exceed the above minimum guiding catheter requirements for Absorb BVS (i.e., only the 7-in-8 GuideLiner provides an adequate inner diameter (0.071" ID), 8F guide catheter would be required).
- For XIENCE, please follow IFU for the guiding catheter size.

Baseline Angiogram and Identification of the potential target lesion:

- Assessment of the potential target lesion(s) to be treated must be done to ensure angiographic criteria are met; this must occur prior to pre-dilatation and vessel sizing.

Pre-dilatation of potential target lesion

- Pre-dilatation of the potential target lesions(s) must be performed.
- Pre-dilatation must be performed with an angioplasty balloon; cutting or scoring balloons may be used per physician discretion, if the lesion appears to be mildly calcified.
- The pre-dilatation balloon should be sized 1:1 to the visually estimated RVD or 0.25 mm smaller than RVD. It cannot be more than 0.5 mm smaller than the visually estimated RVD of the target vessel. If pre-dilatation balloon is sized 1:1, a non-compliant balloon is strongly recommended.

The pre-dilatation balloon must be equal in length or shorter than the planned scaffold/stent length.

Important: Full balloon expansion with the pre-dilatation balloon must be achieved before the patient is randomized into the study. If there is any question that the target lesion was not fully dilated or that any significant resistance to expansion from the lesion remains, the lesion should be re-dilated with a non-compliant balloon (sized 1:1 to the RVD) at higher pressure. Absorb BVS or XIENCE must not be implanted in a lesion in which full balloon expansion has not been achieved.

- The potential target lesion must continue to meet angiographic criteria following adequate pre-dilatation, to be regarded as “successful pre-dilatation”.
 - For randomized subjects, RVD remains ≥ 2.50 mm - ≤ 3.75 mm, and length of the lesion that will be covered by the device (including any edge dissections) is still ≤ 24 mm.
 - For Lead-In subjects, RVD remains ≥ 2.75 mm - ≤ 3.25 mm, and length of the lesion that will be covered by the device (including any edge dissections) is still ≥ 8 - ≤ 14 mm.
 - Residual %DS is a maximum of $< 40\%$ (per visual estimation), $\leq 20\%$ is strongly recommended.
 - TIMI Grade-3 flow (per visual estimation).
 - No angiographic complications (e.g. distal embolization, side branch closure).
 - No dissections NHLBI grade D-F.
 - No chest pain lasting > 5 minutes.
 - No ST depression or elevation lasting > 5 minutes.
- For two potential target lesions, the lesion with the higher possibility of failing vessel sizing criteria (per investigator’s assessment) should be identified as the first target lesion and pre-dilated first before randomization.
 - If pre-dilatation of the 1st target lesion fails, the patient may not be randomized, and the interactive voice response system (IVRS) must not be called.
 - If the 1st target lesion was successfully pre-dilated and vessel sizing criteria are still met, the IVRS is called to randomize the subject. Once the first lesion is successfully treated³² with the assigned device (and only at this time), the second target lesion must be pre-dilated, and then treated with the assigned device.
 - If the 1st target lesion was successfully pre-dilated but did not meet vessel sizing criteria, treat as a non-target lesion. Once the first lesion is successfully treated as a non-target lesion, the second lesion must be treated as the target lesion in which successful pre-dilatation and vessel sizing criteria must be met after which IVRS must be called and the target lesion treated per assignment. If 2nd target lesion fails pre-dilatation and vessel sizing criteria, it should be treated as non-target lesion and subject must not be randomized.
- Each target vessel and lesion should also be such that the operator believes either the Absorb BVS or XIENCE devices could be delivered to and cross the target lesion without additional lesion preparation (e.g., absence of excessive vessel or lesion tortuosity or calcification).

³² Successful lesion treatment is defined as final diameter stenosis $\leq 30\%$ with final TIMI-3 flow, with no residual dissection NHLBI grade \geq type B, and no transient or sustained angiographic complications (e.g. distal embolization, side branch closure), no chest pain lasting > 5 minutes, and no ST segment elevation or depression lasting > 5 minutes.

Vessel Sizing

- Following the use of nitroglycerine (at least 100 µg intracoronary nitroglycerine, >150 µg preferred)³³ and successful pre-dilatation of the potential target lesion(s), vessel sizing must be conducted by visual estimation. Quantitative methods such as on-line QCA, IVUS or OCT may be used per physician discretion but are not required; taking into account that QCA tends to under-estimate RVD compared to visual estimation, whereas IVUS tends to over-estimate lumen RVD compared to visual estimation. Follow core laboratory guidelines for the use of each modality.
- Prior to randomization, IVUS or OCT can be used to evaluate the vessel if there is question regarding the eligibility of the vessel either before or after pre-dilatation.
- A subject must not be randomized in ABSORB III if
 - Vessel size or lesion length before or after pre-dilatation does not satisfy eligibility criteria.
 - Moderate or heavy calcification, tortuosity or other conditions are present proximal or within the target segment, reducing the likelihood that the Absorb BVS or XIENCE can be either delivered to or expanded at the lesion.
 - Complications and/or adverse events were identified during IVUS or OCT usage (e.g., vessel dissection NHLBI grade D-F).³⁴
- Table 7.2 provides the guidance of vessel and device sizing during the procedure, which are detailed as the followings:
 - First, assess RVD based on visual estimation
 - Then, select a pre-dilatation balloon sized 1:1 to RVD or 0.25 mm smaller than RVD. For example, for RVD of 2.5 mm, a pre-dilatation balloon of 2.25-2.5 mm should be used.
 - Use the size of the inflated pre-dilatation balloon, as well as the results after pre-dilatation, to reassess the RVD for appropriate vessel sizing for the scaffold or stent. If the reassessed RVD after pre-dilatation exceeds the specified range for a specific BVS size, the next available size Absorb BVS can be used. For example, if the RVD is reassessed as 2.8 mm after pre-dilatation of a vessel that was believed to be 2.5 mm before pre-dilatation, then implant a 3.0 mm BVS.
 - Post-dilatation must always be a non-compliant balloon. Always make sure the non-compliant post-dilatation balloon has a length short enough so it is inflated within the scaffold margins to avoid edge dissection.

³³ If the patient's blood pressure is so low that ≥ 100 µg of nitroglycerine cannot be administered, the patient should not be randomized. It is suggested that ≥ 200 µg of nitroglycerine be administered if the systolic blood pressure is >140 mmHg. Timing of nitroglycerine administration and pre-dilatation is per physician discretion, but must be before randomization and assessment of scaffold or stent size.

³⁴ Examples of complications associated with IVUS or OCT: side-branch occlusion, persistent S-T abnormalities, prolonged chest pain, flow limiting dissections etc.

Table 7.2 Vessel and Device Sizing

Closest RVD by Visual Estimation	Pre-dilatation Balloon Diameter	Reassessed Closest RVD after Pre-dilatation	Absorb BVS Diameter
2.5 mm	2.25 or 2.5 mm	2.5 mm	2.5 mm
2.75 mm	2.25 – 2.75 mm	2.75 mm	3.0 mm
3.0 mm	2.5 – 3.0 mm	3.0 mm	3.0 mm
3.25 mm	2.75 – 3.25 mm	3.25 mm	3.5 mm
3.5 mm	3.0 – 3.5 mm	3.5 mm	3.5 mm
3.75 mm	3.25 – 3.75 mm	3.75 mm	3.5 mm

Randomization

- Upon successful treatment of the non-target lesion (if any) and completion of successful pre-dilatation and vessel sizing of the first target lesion, interactive voice response system (IVRS) can be called.
- A subject is considered registered and in the ITT population at the time of randomization.
- Lead-In subjects will not be randomized but are assigned to Absorb BVS treatment in target lesion(s).

Lesion Treatment

- The length of the Absorb BVS and XIENCE stent should be selected to allow at least 2 mm but less than 4 mm of normal or nearly normal reference vessel at each edge.
- If the Absorb BVS cannot reach or cross the lesion or additional lesion preparation is required, the Absorb BVS must be removed and a new Absorb BVS must be introduced after subsequent pre-dilatation(s) with the same sized or larger non-compliant balloon at higher pressure. Note: the Absorb BVS should not be “Dottered” across the lesion if it does not cross easily.
- If the Absorb BVS is unable to reach or cross the target lesion after multiple attempts (maximum of two Absorb BVS; including additional lesion preparation), a XIENCE stent must be used.
- If XIENCE is unable to reach or cross the target lesion after multiple attempts (including additional lesion preparation), the investigator should treat the lesion per standard of care.
- In the case of two target lesions assigned to the Absorb BVS, if the first lesion is unsuccessfully treated with the Absorb BVS the following must occur:
 - First target lesion must be treated with XIENCE. If the treatment of the 1st target lesion is successfully treated with XIENCE, treat the 2nd target lesion with Absorb BVS.
 - If the treatment of the 1st target lesion is unsuccessful treated with XIENCE, treat the 1st lesion and 2nd lesion per standard of care. The subject must not be treated with a BVS.

- Every attempt must be made that the two lesion treatment occur at the same index procedure as staged procedures are not allowed. However, if a staged procedure does occur BVS must not be used.
- Successful lesion treatment is defined as final diameter stenosis $\leq 30\%$ with final TIMI-3 flow, with no residual dissection NHLBI grade \geq type B, and no transient or sustained angiographic complications (e.g. distal embolization, side branch closure), no chest pain lasting > 5 minutes, and no ST segment elevation or depression lasting > 5 minutes.
- For Absorb BVS, the scaffold should be deployed slowly, by pressurizing the delivery system in 2 atm increments each, over 5 seconds, until the scaffold is completely expanded. Pressure should be maintained for 30 seconds if tolerated by the patient.
- For the Absorb BVS and XIENCE delivery balloon, do not exceed the rated burst pressure (RBP) per the IFU for the individual device.
- Post-dilatation of target lesion or non-target lesion treated with XIENCE should be per standard of care.
- If post-dilatation of the target lesion treated with Absorb BVS is necessary the following guidance is given:
 - A low profile, high pressure, non-compliant, balloon dilatation catheter that has not been previously inflated must be used.
 - The post-dilatation balloon length should be selected such that the balloon stays within the margins of the scaffold so as to avoid an edge dissection.
 - The expanded diameter of the post dilatation balloon must be within the allowable expansion limits of the scaffold. Do not dilate the Absorb BVS beyond the dilatation limit which is 0.5 mm above the nominal diameter. Doing so may result in scaffold damage. Thus, it is highly recommended that the compliance chart of the non-compliant balloon selected must be carefully reviewed prior to dilatation and an appropriate maximum pressure used to ensure that the scaffold is not over-dilated.

Table 3.0 Scaffold Diameter and Maximum Diameter Limit

Nominal Scaffold Diameter	Post Dilatation Maximum Diameter Limit
2.5 mm	3.0 mm
3.0 mm	3.5 mm
3.5 mm	4.0 mm

- The delivery balloon cannot be removed from the body and reinserted and used for post-dilatation
- IVUS or OCT guidance may be used as per standard of care.
- Please refer to the physician training deck for user guidance in handling procedural issues (e.g., difficult in recrossing an implanted scaffold for purposes such as intravascular imaging or post-dilatation if needed).

Imaging Cohort

If subject is in the Imaging Group (See **Appendix VI and Imaging Guidance Document** for further details):

- Post-procedure angiography, IVUS and OCT are required based on respective imaging groups.
- If post-dilatation was performed, post-procedure imaging must be conducted following last balloon inflation.

If two target lesions are treated, post-procedure imaging must be done on the first target lesion after its successful treatment, and then after successful treatment of the 2nd target lesion.

7.3.5 *Bailout Stenting or Alternative Procedures*

Bailout procedures may be performed if the subject experiences:

- Dissection requiring intervention
- Occlusive complication as evidenced by a decrease in target vessel flow
- Chest pain or ischemic changes measured by ECG that do not respond to repeat balloon inflations, medical therapy or lytic agents
- Unplanned additional device is required to cover the target lesion

In the randomized subjects, if a bailout device is required for a target lesion (e.g., for edge dissection), the same device as the implanted device must be used. Overlap of the bailout stent/scaffold with the implanted stent/scaffold should be 1-2 mm. Gaps should be avoided.

- Use Absorb BVS if target lesion is treated with Absorb BVS.
- Use XIENCE if target lesion is treated with XIENCE.
- If a bailout with an Absorb BVS device cannot be delivered to the site of the lesion, the device should be carefully withdrawn and a XIENCE used.
- If an appropriate size Absorb BVS is not available XIENCE can be used.

If during the Lead-In phase a bailout is required, the investigator should use an appropriately sized XIENCE stent and not an Absorb BVS.

The Imaging Cohort subjects that receive metallic stent bailout of an Absorb BVS treated lesion will be required to complete imaging follow-up at the protocol specified time points of 3 years for IVUS or OCT, depending on which imaging group the subject is in. However, the subject's imaging data will not be included in the imaging study analysis and will not be counted towards the associated powered secondary endpoints analysis. These subjects may be replaced by another subject that received an Absorb BVS without metallic stent overlap.

IMPORTANT: It is required that the bailout device be placed so that there is no visible gap between the Absorb BVS and the bailout device. In such a case, at least 1 mm (minimum) to 2 mm (maximum) overlap is required.

IMPORTANT: In the rare event of acute occlusion following Absorb BVS placement, the bailout device should be XIENCE and deployed within the Absorb BVS such that the Absorb BVS is completely covered by the bailout device if this is believed to be in the best interest of the patient.

Although a bailout procedure is not considered a major adverse cardiac event (MACE) unless the subject sustains death, emergent CABG, PCI or MI, such procedures should be avoided unless required for safe subject management.

7.3.6 Final (Post-procedure) Angiography

Angiographic imaging will also be performed after the Absorb BVS or XIENCE stent deployment. Physicians should follow accepted hospital imaging practice to ensure good apposition of the Absorb BVS or XIENCE to the vessel wall. For angiographic imaging, post-implantation images should be captured the same orthogonal views that were used for the pre-procedure images. Intracoronary nitroglycerine should be re-administered before final angiography.

7.3.7 Final (Post-procedure) IVUS and OCT

For subjects not required to have post-procedure imaging, IVUS and OCT may be performed post-procedure if the investigator believes there is incomplete apposition of the device. The procedure will be performed according to the site's standard. However, if malapposition is seen and post-dilatation required, a non-compliant balloon should be used and in the case of Absorb BVS, do not dilate the Absorb BVS beyond the dilatation limit which is 0.5 mm above the nominal diameter. Repeat angiography in orthogonal views must be performed after any additional inflations.

7.3.8 Imaging Assessment

Subjects from the Imaging Cohort will receive angiography (includes vasomotion assessment), IVUS and OCT at pre-specified time-points (**Section 7.5**). Imaging assessments should be conducted per core lab guidelines in the Imaging Guidance Document distributed to each site. Intracoronary nitroglycerine should be given before all imaging runs to avoid spasm and afford maximal luminal dimensions.

Any Imaging Cohort subject that did not receive the assigned Absorb BVS or XIENCE stent will not receive follow-up imaging procedures. These subjects will be clinically followed under the study. If an Imaging Cohort subject had a TLR prior to the imaging follow-up, the imaging data at the time of TLR and at the protocol specified later imaging time points will be analyzed but not included in the imaging endpoint analysis. If an Imaging Cohort subject had a TVR or angiogram prior to the imaging follow-up, the subject will continue to have the protocol specified imaging follow-up and will not be replaced. If an Imaging Cohort subject has two target lesions but only one target lesion was successfully treated with the assigned device, the unsuccessfully treated target lesion must be imaged post-treatment and at the specified follow-up

times only if the assigned study device was implanted for lesion treatment. Imaging Cohort subjects that receive metallic stent bailout of an Absorb BVS treated lesion will be required to complete imaging follow-up at the protocol specified time points of 3 years for IVUS or OCT, depending on which imaging group the subject is in. However, the subject's imaging data will not be included in the imaging study analysis and will not be counted the associated powered secondary endpoints. These subjects may be replaced by another subject that received an Absorb BVS without metallic stent overlap.

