5.3 Additional Secondary Endpoint(s)

In ABSORB III the following clinical secondary endpoints will be analyzed. Secondary imaging endpoints will be analyzed in the Imaging Cohort.

- **Acute Success:** (Combined Clinical/Angiographic Endpoint)
 - Device success (Lesion level analysis)
 - Procedural success (Subject level analysis)
- **Clinical Endpoint** in hospital and at each follow-up point (30 days; 180 days; 1, 2, 3, 4 and 5 years).
 - **Component**
 - Death (Cardiac, Vascular, Non-cardiovascular)
 - Myocardial Infarction
 - Attributable to target vessel (TV-MI)
 - Not attributable to target vessel (NTV-MI)
 - Target Lesion Revascularization (TLR)
 - Ischemia driven TLR (ID-TLR)
 - Non ID TLR (NID-TLR)
 - Target Vessel Revascularization (TVR,)
 - ID TVR
 - Non ID TVR
 - All coronary revascularization
 - **Composite Endpoints**
 - Death/All MI
 - Cardiac Death/All MI
 - Cardiac Death/TV-MI/ID-TLR (TLF)

- Cardiac Death/All MI/ID-TLR (MACE)
- Cardiac Death/All MI/ID-TLR/ID-TVR, non TL (Target Vessel Failure, TVF)
- Death/All MI/All revascularization
- **Scaffold-Thrombosis / Stent Thrombosis (per ARC definition)**
 - Timing (acute, sub-acute, late and very late)
 - Evidence (Definite and Probable)
- **Imaging Endpoints:**

Imaging endpoints will be analyzed on Imaging Cohort subjects only.

- **Angiography:**

All angiographic endpoints will be collected post-procedure and at 3 years

- In-segment²⁵ late loss (LL)
- In-device²⁶ LL
- Proximal LL (proximal defined as 5 mm of tissue proximal to the device placement)
- Distal LL (distal defined as 5 mm of tissue distal to the device placement)
- In-device/in-segment/proximal/distal minimum lumen diameter
- In-device/in-segment/proximal/distal %Diameter Stenosis (DS)
- In-device/in-segment/proximal/distal angiographic binary restenosis
- In-device net gain (change in minimum lumen diameter between 3 years and post-procedure)
- The magnitude of in-stent/scaffold mean lumen diameter change (absolute value) at 3-years follow-up from pre-nitrate to post-nitrate
- The normalized in-stent/scaffold mean lumen diameter change at 3-years follow-up from pre-nitrate to post-nitrate, defined as,

$$\frac{\text{In - Stent/Scaffold Mean Lumen Diameter change}}{(\text{Proximal Mean Lumen Diameter change} + \text{Distal Mean Lumen Diameter change})/2} \times 100\%$$

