7.3.8.4 Vasomotion Assessment

- At the 3-year follow-up, assessment of vessel movement in response to nitroglycerin infusion will be conducted. Please see the Imaging Guidance Document for the details of this assessment.
- Vasomotion assessment should not be assessed under the following conditions, and those subjects may be replaced for the imaging analysis:

- Target lesion treated with Absorb BVS with metallic stent overlap
 - Target lesion undergoing other PCI procedures prior to 3-year imaging follow-up
 - If target lesion has $\geq 50\%$ stenosis at the time of the 3-year assessment and does not clearly require revascularization, FFR should be conducted to determine if lesion is flow limiting. If the lesion is flow limiting and requires revascularization, vasomotion assessment should not be done.
- Details regarding the angiographic assessment of the vessel and timing of nitroglycerine infusion are further detailed in the Imaging Guidance Document.

7.4 *Post-procedure*

7.4.1 *Post-procedure Information to be Recorded*

The following information needs to be obtained between 12 hours following the index procedure and hospital discharge (in-hospital stay is considered to be a maximum of 7 days following the index procedure).

Between 12 hours post-procedure and discharge

- Date of discharge
- Antiplatelet medications
- Chronic concomitant medications
- Adverse Events, if any

7.4.2 *Post-procedure Laboratory and Clinical Tests*

The following laboratory assessments need to be obtained between post-index procedure and hospital discharge. Hospital discharge cannot occur prior to 16 hours to ensure complete post-procedure cardiac enzyme collection.

IMPORTANT: These tests must be performed whether or not they are considered part of the Investigator's standard of clinical practice.

Post-procedure and discharge

- A 12-lead ECG must be obtained between 30-90 minutes post procedure.
- Both Creatine kinase (CK) and Creatine kinase myocardial-band isoenzyme (CK-MB) must be obtained for ALL registered subjects as it will be used for cardiac assessment of subjects post-index procedure
 - Pre-procedure CK and CK-MB draw*
 - First post-procedure CK and CK-MB draw at 6 to 12 hours post-procedure.

- Second post-procedure CK and CK-MB draw at 18-24 hours post-procedure, or at the time of discharge as long as discharge is at or after 16 hours post-procedure**.

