10.4.2 Powered Secondary Endpoint Analyses

Analysis of the Powered Secondary Endpoints for angina, for all revascularization, for ID-TVR, and for diabetic indication will include subjects from the primary analysis group. Pearson's Chi-square test will be used for superiority testing based on the ITT and PTE populations for the powered secondary endpoint for angina. Fisher's exact test will be used for superiority testing based on the ITT and PTE populations for the powered secondary endpoints for all revascularization and for ID-TVR. Analysis of the Imaging Cohort Secondary Endpoints 1 and 2 will include pooled subjects from the Imaging Cohort of ABSORB III and ABSORB Japan. Two sample t-test will be used for superiority testing based on the ITT and PTE populations.

Details of the analyses for the powered secondary endpoints can be found in the statistical analysis plan (SAP).

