Re-narrowing of the artery defined as %DS \geq 50%.

ACC/AHA Classification Scheme of Coronary Lesions: Lesion-Specific Characteristics

Type A Lesions (High Success, >85%; Low Risk)

- Discrete (< 10 mm length)
- Concentric
- Readily accessible
- Nonangulated segment, < 45°
- Smooth contour
- Little or no calcification
- Less than totally occlusive
- Not ostial in location
- No major branch involvement
- Absence of thrombus

Type B Lesions* (Moderate Success, 60-85%; Moderate risk)

- Tubular (10-20 mm length)
- Eccentric
- Moderate tortuosity of proximal segment
- Moderately angulated segment, > 45°, < 90°
- Irregular contour
- Moderate-to-heavy calcification
- Total occlusions < 3 mo old
- Ostial in location
- Bifurcation lesions requiring double guide wires
- Some thrombus present

* Type B1 lesions: One adverse characteristic

* Type B2 lesions: ≥ two adverse characteristics

Type C Lesions (Low Success, <60%; High Risk)

- Diffuse (> 2 cm length)
- Excessive tortuosity of proximal segment
- Extremely angulated segments > 90°
- Total occlusions > 3 mo old
- Inability to protect major side branches
- Degenerated vein grafts with friable lesions

CHRONIC OCCLUSION

Total Occlusion:

An occlusion with no antegrade filling of contrast to the distal segment (TIMI grade 0)

Sub-total Occlusion:

TIMI grade 1, and with collateral filling of the distal segment

MAXIMUM DIAMETER (Dmax)

Dmax refers to maximum lumen diameter evaluated after pre-dilatation within the boundaries of intended scaffold segment.

IN-STENT

Within the margins of the stent.

IN-SCAFFOLD

Within the margins of the scaffold.

IN-SEGMENT

Within the margins of the stent or scaffold and 5 mm proximal and 5 mm distal to the stent or scaffold.

LATE LOSS (LL)

General definition: Calculated as MLD post-procedure – MLD at follow-up

- In-segment Late Loss: in-segment MLD post-procedure – in segment MLD at follow-up
- Proximal Late Loss: proximal MLD post-procedure – proximal MLD at follow-up (proximal defined as within 5 mm of healthy tissue proximal to the device placement)
- Distal Late Loss: distal MLD post-procedure – distal MLD at follow-up (distal defined as within 5 mm of healthy tissue distal to the device placement)
- In-device Late Loss: in-device MLD post-procedure – in-device MLD at follow-up

PERCENT DIAMETER STENOSIS [%DS]

The value calculated as $100 * (1 - \text{MLD}/\text{RVD})$ using the mean values from two orthogonal views (when possible) by QCA.

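### ABSORB III imaging endpoints leave out subjects with a TLR before 3 years, so binary restenosis and late loss are understated and lumen area is tested only in lesions that were not re-treated

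*Protocol*

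**What the plan says.** Section 7.3.8 of the ABSORB III protocol sets the rule for an Imaging Cohort subject who has a TLR before imaging follow-up: "imaging data at the time of TLR and at the protocol specified later imaging time points will be analyzed but not included". Those data stay out of the imaging endpoints. The rule covers both arms and is separate from the metallic-bailout rule in the same section. A subject with a TVR or an angiogram is treated differently: "the subject will continue to have the protocol specified imaging follow-up and will not be replaced".

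The endpoints affected are these.

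- Section 5.3 lists "In-device/in-segment/proximal/distal angiographic binary restenosis", together with late loss, MLD and %DS. It states: "All angiographic endpoints will be collected post-procedure and at 3 years". Appendix II defines binary restenosis as "Re-narrowing of the artery defined as %DS" of at least 50%, with no provision for an earlier TLR.
- Section 5.2 has two powered imaging endpoints: the change in mean lumen area by IVUS from post-procedure to 3 years, and the change in mean lumen diameter from before to after nitrate at 3 years. Both pool ABSORB Japan.
- Section 7.3.8.4 omits the vasomotion test for a "Target lesion undergoing other PCI procedures prior to 3-year imaging follow-up", and for a lesion found flow-limiting and needing revascularization at the 3-year visit. These subjects may be replaced.

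For the powered imaging endpoints, Section 10.4.2 says: "Two sample t-test will be used for superiority testing based on the ITT and PTE populations". Appendix II defines the ITT population as the subjects registered at randomization.

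**The concern.** Appendix II defines TLR as re-intervention for restenosis or another complication of the target lesion. The rule therefore removes a subject largely because the treated lumen failed, which is what binary restenosis, late loss, MLD, %DS and lumen area are meant to measure. A restenosis severe enough to be re-treated before 3 years is not counted as a restenosis. The image that shows it is read and then set aside.

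The lumen area endpoint supports a superiority claim on late lumen enlargement, and the Imaging Cohort objective in Section 3 includes patency. A test restricted after randomization to lesions that were not re-treated does not answer the ITT question that Section 10.4.2 names.

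**Working it through.** There is no plan figure to reproduce. The sample size, effect size, SD and power for the imaging endpoints are blacked out. What follows is illustrative arithmetic.

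**Inputs from the protocol (Section 2.1.9)**

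- Absorb ID-TLR in Cohort B: 6.0% at 2 years (6 of 100), and 4.5% at 3 years in Group 1 (N=44).
- Mean lumen area in Cohort B Group 1 (n=33): 6.53 mm² post-procedure and 6.85 mm² at 2 years, a gain of 0.32 mm².

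**Assumptions**

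- XIENCE TLR is 4%.
- True restenosis is 9% for Absorb and 7% for XIENCE.
- Every TLR is a restenosis.
- XIENCE lumen area does not change in lesions not re-treated.
- Change at TLR, d, is −2 to −4 mm².

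**Binary restenosis**

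With true rate R and TLR rate T, dropping the TLR subjects gives a reported rate of (R − T)/(1 − T).

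- Absorb, T = 6%: (0.09 − 0.06)/0.94 = 3.2%.
- Absorb, T = 4.5%: (0.09 − 0.045)/0.955 = 4.7%.
- XIENCE, T = 4%: (0.07 − 0.04)/0.96 = 3.1%.

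The same point can be made without choosing R. If r is the restenosis rate among subjects free of TLR, counting TLR as restenosis gives T + (1 − T)r. With r assumed to be 2% to 5%, this is 6.4% to 9.3% at T = 4.5%, and 7.9% to 10.7% at T = 6%.

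**Mean lumen area change**

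Dropping TLR subjects raises an arm's mean by T × (m − d), where m is the mean change in lesions not re-treated. The contrast shifts by the difference between the arms.

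- T = 6% against 4%, d = −2: 0.06 × 2.32 − 0.04 × 2 = 0.139 − 0.080 = 0.059 mm².
- T = 6% against 4%, d = −4: 0.06 × 4.32 − 0.04 × 4 = 0.259 − 0.160 = 0.099 mm².
- T = 4.5% against 4%, d = −2: 0.045 × 2.32 − 0.080 = 0.024 mm².
- T = 4.5% against 4%, d = −4: 0.045 × 4.32 − 0.160 = 0.034 mm².

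The shift is zero when both arms have the same TLR rate and the same gap m − d.

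**Numbers of subjects**

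ABSORB III plans about 150 angiographic/IVUS subjects at 2:1, so about 100 Absorb and 50 XIENCE. At these rates the rule removes about 4 to 6 Absorb subjects and 2 XIENCE subjects, before ABSORB Japan is added.

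**The case against.** The exclusion is explicit and its effect on reported restenosis is hard to dispute. Several objections limit how far the point reaches.

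- *A rescuing analysis may exist elsewhere.* The SAP supplied covers ABSORB IV only, and ABSORB III Section 10.4.10 shows no readable text. A sensitivity analysis in the ABSORB III SAP cannot be ruled out. It would still not remove the rule in 7.3.8.
- *The image after re-intervention shows the second treatment.* This is a fair reason to omit the 3-year image. It does not justify setting aside the image at TLR.
- *Vasomotion is different.* A reader might infer that both powered endpoints lose their worst lumens. The second measures response to nitrate, so the selection is real but the direction of bias is undetermined. A lesion first found flow-limiting at the 3-year visit loses only its vasomotion test. It still counts in restenosis, late loss and IVUS.
- *Bias between arms is not automatic.* A reader might infer that the rule favours the device that fails more. That needs unequal TLR rates or unequal lumen loss at TLR, and the documents establish neither.
- *The illustration depends on its inputs.* At 6% TLR the assumed 2-point restenosis difference almost disappears, but only because R − T was set to 3 points in both arms. At 4.5% it remains 4.7% against 3.1%. A 2 to 4 mm² loss is 31% to 61% of a 6.53 mm² mean area and has no support in the documents. The 0.32 mm² gain is a single-arm change (p=0.3515), not the design effect. Some TLRs are for complications other than restenosis.
- *TLR images may be incomplete.* Sections 7.3.8.1 and 7.3.8.2 schedule follow-up QCA and IVUS only at 3 years, so an IVUS value at TLR may not exist. QCA is more likely to exist, because Appendix II has the core laboratory verify the stenosis for a TLR.
- *Failures are not hidden.* TLR, ID-TLR and TLF are reported at every follow-up point under Section 5.3. This does not correct the imaging endpoints.

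**Conclusion.** The point holds for binary restenosis, late loss, MLD, %DS and the powered IVUS mean lumen area change. The rule removes subjects on an outcome-related event, understates binary restenosis and late loss in both arms, and leaves a lumen area test that is not the stated ITT comparison. The understatement of restenosis rests on at least some TLRs being for restenosis. Bias in the contrast between arms is conditional on TLR rates or lumen loss at TLR differing by arm.

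The size is not fixed by the documents. Under the assumptions listed, reported restenosis is about 3.2% to 4.7% against 3.1%, where the truth was set at 9% against 7%, and the lumen area contrast shifts by about 0.02 to 0.10 mm². The documents do not support a claim that the rule erases a real difference or that it favours Absorb. These are secondary endpoints, but two are powered and are meant to support label claims, so the rule should be changed.

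**What to change.** Amend Section 7.3.8 and the matching analysis text as follows.

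1. Count a TLR before 3 years as binary restenosis if %DS at the TLR angiogram is at least 50%, or if there is no readable angiogram.
2. For late loss, MLD and %DS, use the QCA value from before re-intervention where it exists.
3. For IVUS mean lumen area change, keep the planned t-test. Add a pre-specified worst-rank (Wilcoxon) sensitivity analysis with TLR subjects at the worst rank. This needs no IVUS at the TLR.
4. For both powered imaging endpoints, report the number excluded by arm and reason.

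The cost is analysis wording and some programming, with no new visits or subjects. Reported restenosis and lumen change become slightly less favourable. ABSORB Japan data must be handled the same way where its TLR data allow; its rule is not in the documents supplied.
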